5.6. Interim analysis

Not applicable.

6. TABLE PATTERNS

Table1. Distribution of subjects

Distribution of subjects	Group I (proportion, %)	Group II (proportion, %)
Included in the study (screened)	n/N (%)	
Of these:		
Excluded at the screening stage:	n/N (%)	
Randomized	n/N (%)	n/N (%)
Prematurely excluded, out of them:	n/N (%)	n/N (%)
Existence of exclusion criterion #X (description)	n/N (%)	n/N (%)
Population safety	n/N (%)	n/N (%)
ITT population	n/N (%)	n/N (%)
Population PP	n/N (%)	n/N (%)

Table2. Demographic and anthropometric characteristics of subjects at the time of inclusion (safety population)

Group	Parameter	Age (years)	Weight (kg)	Height (cm)	Smoking index (p/y)	Frequency of acute respiratory infections (amount/g)
GROUP I	n					
	M					
	CO					
	min.					
	max.					
	Me					
GROUP II	n					
	M					
	CO					
	min.					
	max.					
	Me					
p (between groups)						

Table3. Distribution of subjects by gender (safety population)

Gender	GROUP I	GROUP II
Male	n/N (%)	n/N (%)
Female	n/N (%)	n/N (%)
p (between groups)		

Table4. Distribution of subjects by race (safety population)

Race	GROUP I	GROUP II
Caucasian	n/N (%)	n/N (%)
Mongoloid	n/N (%)	n/N (%)
Negroid	n/N (%)	n/N (%)
p (between groups)		

Table5. Medical history (safety population)

Parameter	Value	Group I (N =)	Group II (N =)
Diagnosis (chronic disease)	...	n/N (%)	n/N (%)
Diagnosis (according to anamnesis)	...	n/N (%)	n/N (%)
p (between groups)			

Table 6. Methods of nonspecific prevention (safety population)

Type	Frequency	GROUP I	GROUP II
Total subjects		N =	N =
Masks	Yes	n/N (%)	n/N (%)
	No	n/N (%)	n/N (%)
	Sometimes	n/N (%)	n/N (%)
Respirator	Yes	n/N (%)	n/N (%)
	No	n/N (%)	n/N (%)
	Sometimes	n/N (%)	n/N (%)
Gloves	Yes	n/N (%)	n/N (%)
	No	n/N (%)	n/N (%)
	Sometimes	n/N (%)	n/N (%)
Glasses	Yes	n/N (%)	n/N (%)
	No	n/N (%)	n/N (%)
	Sometimes	n/N (%)	n/N (%)
Surgical overalls	Yes	n/N (%)	n/N (%)
	No	n/N (%)	n/N (%)
	Sometimes	n/N (%)	n/N (%)
p (between groups)			

Table 7. Drug allergy (safety population)

	GROUP I	GROUP II
Total subjects	N =	N =
No	n/N (%)	n/N (%)
Yes	n/N (%)	n/N (%)
p (between groups)		

Table 8. Results of the assessment of the incidence rate at the end of the prevention period (ITT/PP/ITT_NV/PP_NV/ITT_NV_BE/PP_NV_BE population)

	GROUP I	GROUP II
Total subjects	N =	N =
ARVI	n/N (%)	n/N (%)
Not sick	n/N (%)	n/N (%)
p (between groups)		

Table 9. Results of the assessment of the incidence of COVID-19 at the end of the prevention period (ITT population, PP)

	GROUP I	GROUP II
Total subjects	N =	N =
COVID-19 (total)	n/N (%)	n/N (%)
Of these: COVID-19 confirmed	n/N (%)	n/N (%)

COVID-19 probable	n/N (%)	n/N (%)
COVID-19 suspicious	n/N (%)	n/N (%)
p (between groups)		

Table 10. Results of the assessment of the incidence rate at the end of the study (ITT population, PP)

	GROUP I	GROUP II
Total subjects	N =	N =
ARVI	n/N (%)	n/N (%)
Not sick		
p (between groups)		

Table 11. Results of the assessment of the incidence of COVID-19 at the end of the study (ITT population, PP)

	GROUP I	GROUP II
Total subjects	N =	N =
COVID-19 (total)	n/N (%)	n/N (%)
Of these: COVID-19 confirmed	n/N (%)	n/N (%)
COVID-19 probable	n/N (%)	n/N (%)
COVID-19 suspicious	n/N (%)	n/N (%)
p (between groups)		

Table 12. Results of the assessment of the frequency of complicated course (ITT population, PP)

	GROUP I	GROUP II
Total subjects	N =	N =
Complications (total)	n/N (%)	n/N (%)
Of these: ...	n/N (%)	n/N (%)
...	n/N (%)	n/N (%)
p (between groups)		

Table 13. Results of evaluation of the frequency of different scores on the WHO scale at the end of the prevention period (ITT population, PP)

	GROUP I	GROUP II
Total subjects	N =	N =
0	n/N (%)	n/N (%)
1	n/N (%)	n/N (%)
2	n/N (%)	n/N (%)
3	n/N (%)	n/N (%)
4	n/N (%)	n/N (%)
5	n/N (%)	n/N (%)
6	n/N (%)	n/N (%)
7	n/N (%)	n/N (%)
8	n/N (%)	n/N (%)
p (between groups)		

Table 14. Results of evaluation of the frequency of different scores on the WHO scale at the end of the study (ITT population, PP)

Total subjects	GROUP I		GROUP II	
	N =	N =	N =	N =
0	n/N (%)		n/N (%)	
1	n/N (%)		n/N (%)	
2	n/N (%)		n/N (%)	
3	n/N (%)		n/N (%)	
4	n/N (%)		n/N (%)	
5	n/N (%)		n/N (%)	
6	n/N (%)		n/N (%)	
7	n/N (%)		n/N (%)	
8	n/N (%)		n/N (%)	
p (between groups)				

Table 15. Duration of symptoms of the disease (ITT population, PP)

Evaluation period	Parameter	GROUP I	GROUP II
At the end of the prevention period (28 days)	n		
	M		
	CO		
	min.		
	max.		
	Me		
At the end of the study (2 months)	n		
	M		
	CO		
	min.		
	max.		
	Me		
p (between groups)			

Table 16. Distribution of the nature of the symptoms of the disease (ITT population, PP)

Group	Symptom	Number of patients, percentage (%)
GROUP I		n/N (%)
GROUP II		n/N (%)
p (between groups)		

Table 17. Assessment of vital signs (safety population)

Visit	Group	Parameter	SBP (mmHg)	DBP (mmHg)	HR (beats/min)	RR (/min)	Temperature (°C)	Oxygenation (SpO ₂)
B0	GROUP I	n						
		M						
		CO						
		min.						
		max.						
		Me						
	GROUP II	N						
		M						
		CO						

Visit	Group	Parameter	SBP (mmHg)	DBP (mmHg)	HR (beats/min)	RR (/min)	Temperature (°C)	Oxygenation (SpO ₂)
		min.						
		max.						
		Me						
	p (between groups)							
	B3	N						
		M						
	GROUP I	CO						
		min.						
		max.						
		Me						
	GROUP II	N						
		M						
		CO						
		min.						
		max.						
		Me						
p (between groups)								

Table 18. Total number of AE, SAE in groups (safety population)

Group	AE	SAE
GROUP I	n/N (%)	n/N (%)
GROUP II	n/N (%)	n/N (%)
p (between groups)		

Table 19. Number of subjects with reported adverse events (safety population)

Group	AE+	AE-
GROUP I	n/N (%)	n/N (%)
GROUP II	n/N (%)	n/N (%)
p (between groups)		

Table 20. Adverse events that developed in the study group participants (safety population)

N	Mild AE		Moderate AE		Severe AE		Total		Total
	Organ system / AE	C	HC	C	HC	C	HC	C	HC
Organ system x	n/N (%)								
AE x	NN1 NN2 NNX								

Note: the table shows all the AE that chronologically occurred in the group after at least one use of the study drug.

C – related to the study drug

HC – not related to the drug under study

NNx – participant's number with the corresponding AE

Table 21. Adverse events that have developed in the subjects of the control group (safety population)

N	Mild AE	Moderate AE	Severe AE	Total

Organ system / AE	C	HC	C	HC	C	HC	C + HC
Organ system x	n/N (%)						
AE x	NN1 NN2 NNX						

Note: The table shows all AE that occurred in the control group at any time after randomization into the study.

NNx – participant's number with the corresponding AE

Table 22. Adverse events by nosology (safety population)

SOC	PT	Group 1	Group X
Category SOC 1	Category PT 1	n/N (%)	n/N (%)
	Category PT x	n/N (%)	n/N (%)
Category SOC x	Category PT 1	n/N (%)	n/N (%)
	Category PT x	n/N (%)	n/N (%)

Table 23. Severity of AE (safety population)

Group	Mild	Moderate	Severe
GROUP I	n/N (%)	n/N (%)	n/N (%)
GROUP II	n/N (%)	n/N (%)	n/N (%)

Table 24. Results of comparison of groups by vaccination status against COVID-19 (ITT/PP/ITT_NV/PP_NV/ITT_NV_BE/PP_NV_BE population)

	GROUP I	GROUP II
Total subjects	N	N
Not vaccinated	n/N (%)	n/N (%)
Vaccinated	n/N (%)	n/N (%)
p (between groups)

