¹² Death is an outcome, not the SAE itself, so such a name should not appear as a name. If a case of death for an unknown reason is identified, researcher should make every effort to identify its suspected causes. SAE in such cases can be referred to as "Death by unexplained cause" only in cases where the causes of death are not known and cannot be clarified. In case of a fatal outcome due to COVID-19, the information is recorded in the primary medical documentation of the study participant without registration of the SAE.

¹³ The term "Life threatening" in this context means that the volunteer participating in the study was at immediate risk of death during the occurrence of adverse event. This term does not apply to cases where adverse event could hypothetically cause the death of a participant if it were more intense in severity or longer in duration.

¹⁴ Hospitalization for optional or pre-planned treatment of concomitant diseases that the participant had prior to inclusion in the study, the course of which did not worsen during participation in the study, is not considered to SAE, as well as being in a hospital for less than 24 hours or hospitalization for social reasons.

¹⁵ Pregnancy cases in the participants of the clinical study are not subject to registration as AE, except in cases when the child has congenital anomaly or malformation (case is registered as AE).

same time, when closing AE registration form, maximum severity of AE is indicated, which was observed for the entire period of AE persistence as part of the subject's participation in the study.

Recurrent AE – AE, which was completely resolved, for example, during one cycle of therapy, and then reappeared, for example, on the next cycle of therapy, while the participant is in the study. Each recurrent AE is registered separately.

All AE are registered in the primary medical documentation of the participant based on physical examination, survey, and diary records. The following information must be recorded in the primary medical documentation (outpatient card) for each AE:

- severity (mild, moderate, severe);
- nature of adverse event;
- relationship with study drug;
- duration (date of occurrence and end date), preferably with an indication of the time interval (hours) from the moment of administration of the study drug;
- whether adverse event is serious.

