2. CLINICAL TRIAL DESIGN

2.1. Design

Post-marketing non-interventional prospective randomized open-label comparative study.

A total of 4 visits are planned (0–3). Visit 0 and 1 can be combined.

During randomization, participants are randomly distributed in a 1:1 ratio into two groups:

[figure not shown]
Group I (main) and Group II (control).

According to the methodology approved by this protocol, the participant must use (Group I) or not use (Group II) study drug (depending on the distributed randomization number at Visit 1) for 27 days of the preventive course (10 days + 7 days + 10 days).

The effectiveness of preventive therapy will be recorded. The presence and severity of any adverse events and events will also be evaluated, regardless of the alleged connection with the use of the study drug Ingaron®.

The schedule of visits and procedures is identical for all study participants. A detailed description of the research procedures is provided in the Protocol.

The schedule of research procedures is presented in the section DESIGN of NON-INTERVENTIONAL RESEARCH Protocol. The study periods with the planned time are shown in the diagram below:

Scheme 1. Design

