5. STATISTICAL DATA PROCESSING

5.1. Statistical methods of analysis

To create conditions for an independent evaluation of the results obtained, statistical data processing at the end of the study will be carried out by employees who are not related to the management of the subjects participating in the study. The primary data base was created in Excel when processing registration cards received from the clinical center. Data processing will be performed in the software environment of the R package (R: A language and environment for statistical computing. R Core Team. R Foundation for Statistical Computing, Vienna, Austria)⁶ version 4.1.0 using "A Guidance Document for the Use of R in Regulated Clinical Trial Environments"⁷.

Descriptive statistics are presented for all baseline indicators collected during the study for all subjects included in the study (safety-population). The distribution of subjects, demographic and initial characteristics are presented using descriptive statistics methods.

For numerical indicators, such as demographic and anthropometric data (body weight, age, height, BMI), as well as numerical performance parameters will be calculated:

- Number of missing values (N);
- Minimum value (Min);
- Maximum value (Max);
- Arithmetic Mean (M);
- Standard Deviation (SD);
- Median (Me).

For qualitative variables (frequency of AE/SAE development, for example), absolute number in the n/N format will be given, as well as the percentage (%).

Verification of the normality of the distribution will be carried out by one of the generally accepted methods (visualization of data in a dot diagram in combination with the calculation of the Kolmogorov-Smirnov test, as well as the test for asymmetry and kurtosis).

In the case of a normal distribution, an intergroup comparison of quantitative characteristics will be carried out using the t-test (or the Mann-Whitney test otherwise). For categorical data, the χ^2 -criterion or the exact Fisher test will be applied if the expected frequency in any of the cells is less than 5.

If statistically significant differences between the groups are found, the magnitude of the differences between the study groups will be estimated using confidence intervals. Significance levels and confidence intervals will be calculated as two-sided, and the statistical significance of the differences is by default two-sided and refers to a significance level of 0.05.

Correction for multiple comparisons is not required.

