- Frequency of development of complicated course of ARVI.

The proportion of patients will be presented as a frequency, a percentage in % indicating a bilateral 95% CI, measured according to the data recorded at the time of the corresponding measurement period. For a comparative analysis of the proportions between the groups, method of a two-sided version of the Fisher's exact test (with expected frequencies less than 5) or the Pearson chi-squared test ($2\chi^2$) (with the Yates correction for expected frequencies more than 5, but less than 10) will be used.

The analysis of secondary performance parameters will be carried out both on the ITT population (main analysis) and on the PP population (additional analysis).

Analysis of safety parameters

The study plans to analyze the following security variables:

- frequency of AE/SAE registration in treatment groups (in general and by organ systems);
- changes in vital signs (heart rate, blood pressure, body temperature, respiration rate and SpO₂) during the study (by visits and groups).

For categorical safety indicators in each group and for each visit, according to the survey scheme of participants, frequency, percentage in% and bilateral 95% CI will be calculated. Comparing groups by categorical indicators with the number of categories less than 5, Fisher's exact test will be used, otherwise Pearson chi-squared test (χ^2) will be used (with Yates correction for expected frequencies of more than 5, but less than 10).

The results of measuring vital signs (assessment of heart rate, respiration rate, blood pressure, body temperature and SpO₂) will be presented by treatment groups using descriptive statistics.

The analysis of safety parameters will be carried out on the safety population.

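### SAP Table 18 puts a percentage and a between-group p-value on what read as adverse event counts, so repeat events in one participant would be tested as if independent; the flaw is minor and confined to that table

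*SAP*

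**What the plan says.** SAP section 6 contains the shell "Table 18. Total number of AE, SAE in groups (safety population"), with AE and SAE columns, n/N (%) cells and a p row between groups. The next shell is "Table 19. Number of subjects with reported adverse events (safety population"). It splits each group into AE+ and AE- and has its own p row. It has no SAE column.

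SAP section 5.1 lists the safety variable as "frequency of AE/SAE registration in treatment groups (in general and by organ systems"), without saying whether events or participants are counted. For qualitative variables, "absolute number in the n/N format will be given, as well as the percentage"; N is not defined for Table 18. The tests for categorical safety data are given as follows: "Comparing groups by categorical indicators with the number of categories less than 5, Fisher's exact test will be used", and otherwise Pearson's chi-squared with a Yates correction for small expected frequencies. On level and sidedness, "the statistical significance of the differences is by default two-sided and refers to a significance level of 0.05". No method for counts, rates or clustered events is named.

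In the Protocol's safety criteria, the definition of a recurrent AE ends: "Each recurrent AE is registered separately".

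**The concern.** Fisher's and Pearson's tests need one independent yes/no outcome per unit. If n in Table 18 is a number of events and N a number of participants, n/N is not a proportion and could exceed 100%. Someone with four events then carries the weight of four people. The test's variance is too small, and a few participants with many events can produce a nominally significant difference.

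Safety is the trial's secondary objective. Table 18's SAE column is the only planned between-group comparison of SAEs. For AEs, the report could carry two conflicting p-values, from Tables 18 and 19, with no rule on which governs.

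**Working it through.** Table 18 is an empty shell, so there is no stated figure to reproduce. The check has two parts: what the table counts, and what the named tests do with such counts.

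**What Table 18 counts.** If it counted participants, its AE column would repeat the AE+ column of Table 19. The two shells differ only if Table 18 counts events. One participant can supply several, because recurrences are registered separately.

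**Inputs from the documents.** 315 randomized per group (SAP 5.2); equal allocation, since "participants are randomly distributed in a 1:1 ratio into two groups" (SAP 2.1); two-sided 0.05 (SAP 5.1). **Assumed**, because the documents give none: m, the mean number of AEs per person, and φ, the variance/mean ratio of that number.

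**Approximation, N = participants.** With no true difference:
- True variance of the difference in n/N: 2φm/N.
- Variance used by the 2×2 test: 2m(1−m)/N.
- The z statistic is too large by k = √[φ/(1−m)], so true rejection = 2[1 − Φ(1.96/k)], where Φ is the normal distribution function.

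| m | φ | k | 1.96/k | Rejection |
|---|---|---|---|---|
| 0.05 | 1 | 1.026 | 1.910 | 5.6% |
| 0.05 | 1.5 | 1.257 | 1.560 | 11.9% |
| 0.05 | 2 | 1.451 | 1.351 | 17.7% |
| 0.1 | 1.5 | 1.291 | 1.518 | 12.9% |
| 0.1 | 2 | 1.491 | 1.315 | 18.9% |
| 0.5 | 3 | 2.449 | 0.800 | 42.4% |

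If nobody has more than one AE, then φ = 1−m, k = 1, and rejection is 5%.

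**N = all events.** If N were the total number of events, the test would compare each group's share. Then k = √φ. For φ = 1.5 this gives 1.96/1.225 = 1.600 and 11.0%; for φ = 3, 1.96/1.732 = 1.132 and 25.8%. This reading fails too.

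**Simulation.** 4,000 null trials per setting, 315 per group, with the test chosen by expected frequency: Fisher below 5, Yates-corrected chi-squared from 5 to 10, otherwise chi-squared. This is the SAP's wording for proportions, applied here to safety. The entries are rejection rates of the event-count test.

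| Participants with an AE | Mean 1 event per affected person | 1.5 | 2 | 3 |
|---|---|---|---|---|
| 5% | 4.6% | 15.5% | 25.0% | 34.2% |
| 10% | 5.6% | 17.0% | 25.5% | 37.1% |
| 20% | not run | 17.9% | 29.7% | not run |

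The same rule applied to participants with at least one AE rejected in 4.4% to 5.9% of trials throughout.

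**Worked example (invented counts).** z = (difference/315) / √[p(1−p)·2/315], with p the pooled proportion.
- Participants, 22 v 18: p = 40/630 = 0.0635, z = 0.654, P = 0.51.
- The same people with 44 v 22 events: p = 66/630 = 0.1048, z = 2.862, P = 0.004.

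**The case against.** **The event reading is inferred.** The SAP never defines n or N for Table 18. Its general text gives the frequency of AE/SAE development as an example of a qualitative variable, and the n/N (%) format suits participants. That is fair: the reading is a strong inference, not a stated fact. But a participant reading would make the AE column redundant, and n and N would still need defining.

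**Other rules limit repeat counting.** The Protocol registers a persistent AE once, does not require separate entries for the symptoms of one disease, and does not treat symptoms of acute respiratory infection as AEs. These rules reduce clustering. They do not remove it, since recurrences and unrelated AEs in one person still count separately.

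**The inflation may be small.** The Protocol does not expect the injectable form's side effects intranasally, so low rates are plausible. The safety paragraph, read literally, also assigns Fisher's test to any indicator with fewer than five categories. With Fisher throughout, simulated rejection for φ from 1 to 1.5 is 3.4% to 8.5% at m = 0.05 and 4.6% to 10.6% at m = 0.1. At an assumed 0.01 SAEs per person it is 1.4% to 3.9%, below nominal. This stands as a limit on size; at m = 0.1 and φ = 3, Fisher still rejects in 25%.

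**A stronger reading to avoid.** A reader might infer that the trial's safety p-values as a whole are invalid. The documents do not support that: Table 19 already plans a participant-level comparison for any AE, with its own p-value, on the same population.

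**Conclusion.** Wrong as written, but minor: a secondary safety table. The Table 18 p-value treats repeat events in one participant as independent, and its percentage is not a proportion of participants. Its type I error exceeds 5% when AEs recur and is nominal if no one has more than one.

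The size cannot be fixed from the documents. Under assumed rates it runs from roughly nominal (low rates, no clustering), through about 12 to 19% (0.05 to 0.1 AEs per person, variance/mean 1.5 to 2), to about 42% (0.5 per person, variance/mean 3). Quoting only the upper part of that range would overstate the case.

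The conclusion rests on reading Table 18 as events and on applying the only tests the SAP names. Table 19's any-AE p-value and the primary endpoint are unaffected. The remaining gap is that no participant-level SAE comparison is planned; if SAEs are rare and seldom repeat, its practical effect is small.

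**What to change.** 1. In Table 18, define n as the number of events. Show event counts, and events per participant, descriptively. Delete the percentage and the p row.
2. Extend Table 19 to participants with and without at least one SAE.
3. Add one sentence to the safety analysis in SAP 5.1: every between-group test of AEs or SAEs is based on participants with at least one event.

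Count models, bootstrap methods and risk differences for each organ system are optional; the flaw does not require them. The cost is two table shells and one sentence, with no new data.
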